#### b. Causality:

A **Related or Possibly Related Adverse Event** will be defined as any adverse event for which there is a "reasonable possibility" of a causal relationship between the study drug or study procedure and the adverse event. For each recorded adverse event, investigators will grade the strength of the relationship of study drug or study procedure to the adverse event, as follows:

- **Definitely Related:** The adverse event meets all three of the following criteria: (a) a temporal sequence from receipt of study drug or study procedure to the adverse event suggests relatedness, (b) the event cannot be explained by the known characteristics of the patient's clinical state or other therapies, and (c) evaluation of the patient's clinical state indicates to the investigator the experience is definitely related to study drug or study procedures.
- **Possibly Related:** In the investigator's opinion, the adverse event is possibly related to study procedures but one or more of the above criteria for "Definitely Related" are not met.
- **Probably Not Related:** The adverse event occurred while the patient was on the study but, in the opinion of the investigator, can reasonably be explained by the known characteristics of the patient's clinical state or other therapies.
- **Definitely Not Related:** The adverse event was definitely produced by the patient's clinical state or by other therapies and not by the study drug or study procedures.
- **Uncertain Relationship:** The adverse event does not meet any of the criteria previously outlined.

#### c. Expectedness:

An **Unexpected Adverse Event** is defined as an adverse event that is not listed in the investigator brochure or study protocol or is not listed at the specificity or severity that has been observed.

**d. Severity:**

The investigator will evaluate all AEs with respect to both seriousness (defined in 13.1.a. above) and **severity** (intensity or grade). AEs will be graded for severity according to the *DAIDS Table for Grading the Severity of Adult and Pediatric Adverse Events* (also known as the DAIDS AE Grading Table). For specific events that are not included in the DAIDS AE Grading Table, the generic scale listed below is to be used:

**Generic AE Grading Scale**

Grade 1	Events causing no or minimal interference with usual social and functional activities, and NOT raising a concern, and NOT requiring a medical intervention/ therapy.
Grade 2	Events causing greater than minimal interference with usual social and functional activities; some assistance may be needed; no or minimal medical intervention/therapy required.
Grade 3	Events causing inability to perform usual social and functional activities; some assistance usually required; medical intervention/therapy required.
Grade 4	Events causing inability to perform basic self-care functions; medical or operative intervention indicated to prevent permanent impairment, persistent disability, or death.
Grade 5	Events resulting in death.

**An Adverse Event of Special Interest (AESI)** will be defined as a pre-specified event of scientific or medical concern that has the potential of being related to study drug and is important to understand regardless of investigator classifications. AESIs included below will be recorded in the adverse event eCRF and will require a written narrative.

**13.2 Protocol-specified exempt serious events (PSESEs)**

Outcomes of acute respiratory infection, COVID-19, and critical illness will be systematically collected as Protocol-specified exempt serious events (PSESEs) for all patients.

**PSESEs are exempt from adverse event reporting unless:**

1. the event is determined to be Serious and Definitely or Possibly Related to the study drug or study procedures;
2. the event is determined to be Unexpected and Definitely or Possibly Related to the study drug or study procedures; or

This approach is taken to avoid creating an overly cumbersome safety oversight environment by identifying expected clinical outcomes as safety events and obscuring real safety signals. Even as they are exempted from expedited reporting requirements, PSESEs will be reviewed regularly (unblinded, by treatment arm) by the DSMB to maintain the integrity of safety monitoring for the trial. PSESEs that meet none of the criteria above will not be recorded or reported as AEs.

PSESEs may occur during the initial hospitalization, lead to a re-admission, or occur in a later hospitalization during follow-up. The following are study-specific exempt serious events:

- Death (not Definitely or Possibly Related to the study drug or study procedures)
- Neurological Events:
  - Seizure

- Stroke
- Cardiovascular Events:
  - Hypotension as defined by low arterial blood pressure leading to either [1] initiation or increase in vasopressor therapy, [2] administration of a fluid bolus of 500 ml or more, or [3] modification of the dose or discontinuation of the study drug.
  - Atrial or ventricular arrhythmia
  - Cardiomyopathy
  - Cardiac arrest
  - Myocardial injury
  - Acute coronary syndrome
  - Hypertension as defined by elevated arterial blood pressure leading to either [1] initiation or increase in antihypertensive medications or [2] discontinuation of the study drug
- Respiratory events:
  - Hypoxemia requiring supplemental oxygen
  - Acute respiratory distress syndrome
  - Receipt of non-invasive or invasive mechanical ventilation
  - Receipt of extra-corporeal membrane oxygenation
- Gastrointestinal events:
  - Elevation in aspartate aminotransferase or alanine aminotransferase
  - Acute pancreatitis
- Renal events:
  - Acute kidney injury
  - Receipt of new renal replacement therapy
- Endocrine events:
  - Symptomatic hypoglycemia
- Hematologic or coagulation events:
  - Neutropenia, lymphopenia, anemia, or thrombocytopenia
  - Venous thromboembolism
- Dermatologic events:
  - Severe dermatologic reaction (e.g., Steven's Johnson Syndrome)

A PSESE for “initiation of vasopressor therapy” should be recorded for patients who newly receive any vasopressor at a dose of at least 0.1 mcg/kg/min norepinephrine equivalents (see table). A PSESE for an “increase in vasopressor therapy” should be recorded for patients receiving a vasopressor at a dose of at least 0.1 mcg/kg/min norepinephrine equivalents who experience a doubling of vasopressor dose compared to either the dose at the time of randomization or the lowest dose in the prior 24 hours.

Drug	Dose	Norepinephrine equivalent
Epinephrine a	0.1 µg/kg/min	0.1 µg/kg/min
Norepinephrine a	0.1 µg/kg/min	0.1 µg/kg/min
Dopamine a	15 µg/kg/min	0.1 µg/kg/min
Phenylephrine b	1.0 µg/kg/min	0.1 µg/kg/min
Vasopressin	0.04 U/min	0.1 µg/kg/min

Note: Consistent with this approach, sites will evaluate a potential adverse event to determine whether it is a PSESE. If it is not a PSESE, it will be recorded and reported as an adverse event as outlined below. If the event is a PSESE, it will be evaluated for relatedness and expectedness. If the event is Serious and Definitely or Possibly Related, Unexpected and Definitely or Possibly Related it will be recorded as both a PSESE and an Adverse Event. If the PSESE does not meet either of these three criteria, then the event will be recorded as a PSESE in the PSESE eCRF as a study outcome. A study-specific clinical outcome may also qualify as a reportable adverse event. For example, a ventricular arrhythmia the investigator considers Serious and Definitely or Possibly Related to the study drug would be both recorded as a study-specific clinical outcome and reported as a Serious and Definitely or Possibly Related Adverse Event.

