- Adverse Events that are Serious OR are Definitely or Possibly Related (or of Uncertain Relationship) OR are a Grade 3 or 4 Clinical AE (isolated laboratory abnormalities that are not associated with signs or symptoms are not collected)

We outline the safety data collected in Table 2.

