***22.8 Fostamatinib Arm Logistics***

The use of fostamatinib for the proposed indication is investigational and the study will be conducted under FDA IND #154000 and will cross reference IND #152131. Fostamatinib can be stored at room temperature, 20°C to 25°C (68°F to 77°F); excursions permitted between 0°C to 40°C (32°F to 104°F). Rigel has adequate investigational product and placebo to enroll 300 active and 300 placebo patients.

For regulatory reporting purposes, including identification and potential expedited reporting of 'SUSAR' events, the following serious and/or non-serious Adverse Events/Reactions are among the events that are considered expected for this study:

- Neutropenia
- Diarrhea
- Elevated AST, ALT, or bilirubin. However, AST or ALT greater than 10 times the local laboratory ULN or the baseline value at the time of randomization, whichever is greater, is considered unexpected for fostamatinib study drug for the purposes of adverse event reporting.
- Hypertension

The following is considered an AESI for the fostamatinib arm:

- AST or ALT greater than 5 times the local laboratory ULN or the baseline value at the time of randomization, whichever is greater

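### Protocol Sections 13.1 and 13.3 conflict with 13.2 on whether the fostamatinib hepatic AESI goes in the AE eCRF, so its count and narratives can be incomplete or differ between sites

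*Protocol*

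**What the plan says.** **AESI rule.** Protocol 13.1 defines an AESI as an event that "is important to understand regardless of investigator classifications", and adds: "AESIs included below will be recorded in the adverse event eCRF and will require a written narrative". Section 13.3, which lists what goes on the AE form, includes AESIs with a narrative and attaches no PSESE condition to them.

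**The fostamatinib AESI.** Section 22.8 names one: "AST or ALT greater than 5 times the local laboratory ULN or the baseline value at the time of randomization, whichever is greater". The same section treats AST/ALT elevation as expected, and as unexpected only above 10 times the same reference.

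**PSESE rule.** The PSESE list in Section 13.2 contains "Elevation in aspartate aminotransferase or alanine aminotransferase", with no threshold. A PSESE becomes an AE if it is serious and definitely or possibly related. The second and last printed criterion reads "the event is determined to be Unexpected and Definitely or Possibly Related to the study drug or study procedures; or", and nothing follows the final word. Then comes: "PSESEs that meet none of the criteria above will not be recorded or reported as AEs". The triage note that closes the section begins its last branch with "If the PSESE does not meet either of these three criteria" and sends such events to the PSESE eCRF.

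**Laboratory remark.** In Section 13, the item on serious, related or Grade 3 or 4 clinical AEs carries a parenthesis: "isolated laboratory abnormalities that are not associated with signs or symptoms are not collected".

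**The concern.** An AESI is meant to be captured in a fixed way, whatever the site thinks about cause or seriousness. The PSESE exemption turns on exactly those judgements. Both rules apply to the same enzyme rise, and the protocol does not say which prevails.

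A site that follows 13.1 and 13.3 makes an AE entry and writes a narrative. A site that follows 13.2 and its triage note makes a PSESE entry only. At stake are the completeness of the AESI count above 5 times and of its narratives, and their comparability across sites. This is the only event that the fostamatinib appendix singles out in this way.

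**Working it through.** No arithmetic applies. The check traces an AST or ALT value above 5 times the reference (the greater of ULN and baseline) through each rule as printed.

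| Size of rise | Serious? | Relatedness | Section 13.2 | AESI rule (13.1, 13.3) | Result |
|---|---|---|---|---|---|
| Above 5, up to 10 times | No | Definitely or possibly | Expected under 22.8, so neither criterion is met: no AE entry | AE eCRF and narrative | Conflict |
| Above 5, up to 10 times | Yes | Definitely or possibly | First criterion met: AE entry | AE eCRF and narrative | Agree on entry |
| Above 10 times | Either | Definitely or possibly | Unexpected, second criterion met: AE entry | AE eCRF and narrative | Agree on entry |
| Above 5 times, no upper limit | Either | Probably or definitely not | Neither criterion met: no AE entry | AE eCRF and narrative | Conflict |
| Above 5 times, no upper limit | Either | Uncertain | Category not named in 13.2: no AE entry | AE eCRF and narrative | Conflict |

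In the last row, Section 13.3 adds a further mismatch. Apart from its AESI line, it also records PSESEs of uncertain relationship if they are serious or unexpected, which 13.2 does not provide for.

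**Is there a precedence rule?** None is stated. The triage note asks first whether the event is a PSESE, then about relatedness and expectedness. It has no AESI step.

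**Is the list in 13.2 complete?** It prints two criteria and ends on a conjunction, and the note counts three. One item therefore appears to be missing. The documents do not show what it was, so it cannot be assumed to have been an AESI exception.

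**Where does an exempt event go?**
- It is entered in the PSESE eCRF (Protocol 13.2). PSESEs are collected through Day 60 (Protocol 13 and Table 2).
- The DSMB reviews PSESEs unblinded by arm (Protocol 13.2), and their frequencies are reported (SAP 7.2).
- In the SAP 3.3 safety outcomes it falls in the Other PSESE row, analysed by day 7 and by day 28.

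**Does that route replace the AESI record?** It does not do so fully. The PSESE item has no 5-times threshold and no narrative requirement, and the SAP row pools it with unrelated event types. SAP 7.2 leaves agent-specific safety endpoints to the therapy's appendix. Appendix D defines the AESI but gives no tabulation for it. Whether the PSESE form records the enzyme value is not stated.

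**The case against.** The strongest reply is that the protocol already answers the question. Section 13.3 governs the AE form and lists AESIs without restriction, while the three lines just above each exclude PSESEs. Together with the 13.1 definition, this suggests that the specific AESI rule was meant to override the general exemption. That is probably the intent, but it has to be inferred. Section 13.2 bars the entry without mentioning AESIs, and its triage note gives sites a step-by-step path that bypasses them.

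A second reply is that other routes catch the event. Liver tests are run daily in hospital on study drug. Section 22.7 has stopping criteria starting at 5 times, and Section 7.7.3 sends a stop for a possible event to a reporting page. This stands as evidence that the event will be noticed. But 7.7.3 names the PSESE page or the AE page without saying which applies to an AESI.

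A third reply is that the laboratory remark in Section 13 is not a general ban. That is right: it most naturally explains what a clinical Grade 3 or 4 AE is. It is not independent proof of the conflict, although a site could misread it for a symptom-free enzyme rise.

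It could also be argued that the word serious in the PSESE name keeps non-serious rises off the list. But the first criterion tests seriousness separately, so the list must include non-serious events.

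Finally, the AE recording flow chart (listed as Figure 2) and the manual of procedures were not available for this check. Either may contain an AESI step.

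**Conclusion.** The conflict stands. It covers non-serious rises above 5 and up to 10 times, even if related, and every rise above 5 times judged not related. Uncertain relationship is treated inconsistently as well. For these events a site that follows 13.2 literally omits the AE entry and narrative that 13.1 and 13.3 require.

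Four stronger readings are tempting, and the documents do not support them:
- **The hepatic event goes uncounted.** It stays on the PSESE eCRF, reaches the DSMB by arm and falls within a SAP safety outcome. What can be lost is the AESI-specific count and narrative.
- **It is the drug's main toxicity.** It is the arm's only AESI, but Section 22.5 lists hypertension, diarrhea and neutropenia beside raised liver tests.
- **The conflict covers most of the AESI range.** The range is open above 5 times, and no distribution or event rate is given.
- **Section 13.2 exempts every such rise.** Those that are serious and related, or above 10 times and related, still become AEs.

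The conclusion rests on the printed text and on no override being stated elsewhere. It does not touch randomization, the primary analysis or sample size. It is a wording fault with a real effect on safety recording, and it should be corrected.

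**What to change.** - **Section 13.2, criteria.** Complete the list with an exception: any event that meets an AESI definition in a drug appendix is entered in the AE eCRF with a narrative, as well as in the PSESE eCRF, whatever its seriousness, relatedness or expectedness.
- **Section 13.2, triage note.** Add the AESI step and make the number of criteria agree with the list. Align the handling of uncertain relationship with 13.3.
- **Section 13.** State that the laboratory parenthesis does not apply to AESIs.
- **SAP 3.3 or 7.2.** Add a separate AESI tabulation by arm.

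The cost is protocol wording, a memo to sites, a small increase in AE entries and narratives, and one extra table. Any event already entered only as a PSESE would need to be checked against the AESI definition, which depends on the enzyme values being retrievable.

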### 13.3 Monitoring and recording adverse events

The principal investigator at each study site has the responsibility for the safety of the individual participants under his or her care. For inpatients through day 28, on a daily basis the investigator or designee will determine if any adverse event has occurred. For each adverse event, the investigator will determine whether the adverse event was serious, whether it was definitely or possibly related to study drug or study procedures, whether it was unexpected, and of what severity it was.

The following categories of adverse events will be recorded as AEs in the Adverse Event case report form:

- Adverse Events that Qualify for Expedited Reporting:
  - Serious Unexpected, and Definitely or Possibly Related Adverse Events [also known as “Suspected Unexpected Serious Adverse Reactions” (SUSARs)]- adverse events that are considered by the investigator to be serious, unexpected, and definitely or possibly related to the study drug or study procedures
- Adverse Events that Qualify for Recording and Routine Reporting through Day 60
  - Non-SUSAR adverse events that are ‘Serious and Definitely or Possibly Related or of Uncertain Relationship’ OR that are “Unexpected and Definitely or Possible Related or of Uncertain Relationship”, regardless of whether they are PSESEs
  - Non-SUSAR adverse events that are Serious and are not PSESEs

- Non-SUSAR adverse events that are Definitely Related, Possibly Related, or of Uncertain Relationship and are not PSESEs
- Non-SUSAR adverse events that are Grade 3 or 4 Clinical AEs and are not PSESEs
- AESIs will include a narrative and will be reported in a routine manner

### **13.4 Reporting adverse events**

This section describes the schedule for recording and reporting different types of safety events on eCRFs. In the care of study participants more information may be collected and recorded in the participant's medical record. The information collected in the medical record serves as source documentation of events (e.g., signs, symptoms, diagnoses) considered for reporting on eCRFs as part of protocol data collection.

#### **13.4.1 Adverse Events that Qualify for Expedited Reporting**

Adverse Events that qualify for Expedited Reporting include events that: are Serious, Unexpected and Definitely or Possibly Related (also known as Suspected Unexpected Serious Adverse Reactions, SUSARs). Adverse Events that qualify for Expedited Reporting (SUSARs) must be reported to the coordinating center by site investigators within 24 hours of site investigators becoming aware of the adverse event. The investigator at the study site or designee should inform the clinical coordinating center both by telephone and by official notification via completion of the Adverse Event case report form (Figure 2). The Medical Monitor may discuss with the site PI to determine if this event meets criteria for requiring Expedited Reporting (SUSAR). Events requiring Expedited Reporting (SUSARs) will be reported by the clinical coordinating center to the DSMB, sIRB, FDA and NHLBI within 7 calendar days of receipt of the report from the study site (as well as CA, IECs and other bodies per applicable local regulations for ex-U.S. sites). A copy of the Adverse Event case report form will be sent to the FDA, DSMB, sIRB, and NHLBI and appropriate regulatory bodies for ex-U.S. sites per applicable local regulations within 14 calendar days of receipt of the report from the study site. Adverse Events requiring Expedited Reporting (SUSARs) are followed until the outcome of the Adverse Event is known. If the outcome of an Adverse Events is still unknown at the time of the final follow-up visit, the outcome will be entered in the database as "unknown."

In parallel, non-U.S. participant SAEs should be reported to the NEAT ID Sponsor using the study specific Safety Event Reporting Form (SERF), within 24 hours of a member of the study team becoming aware of the event via e-mail to **[contact]** or via the fax number provided on the SERF.

For non-U.S. participants, processing of relevant safety events, including expedited SAE reporting pertinent to those ex-US territories, including electronic reporting via EudraVigilance of suspected unexpected serious adverse reactions (SUSARs) via ICH E2B compliant safety reports (ICSRs/acknowledgements) will be in line with Directive 2001/20/EC Detailed guidance on the collection, verification and presentation of adverse event/reaction reports arising from clinical trials on medicinal products for human use (CT-3).

Adverse Events, that qualify for recording, but do not qualify for Expedited Reporting (i.e., adverse events that are not SUSARs), will be recorded on the Adverse Event eCRF through day 60. The DSMB will review all recorded adverse events during the scheduled meetings. The clinical coordinating center will distribute the written summary of the DSMB's review including the review of adverse events to the sIRB. If the DSMB determines the overall rate of adverse events is higher in

the intervention group than the control group, the coordinating center will notify the sIRB and the Food and Drug Administration within 14 calendar days of this determination.

All deaths are reported on the eCRF for deaths. Deaths considered **definitely or possibly related to the study intervention** (blinded investigational agent/placebo) must **also** be reported as an AE and may qualify for Expedited Reporting.

All deaths that are felt to be possibly or definitely related to study drug would be unexpected (for reporting purposes).

Unanticipated problems are findings discovered during the conduct of the trial that suggest participation in the trial may have more risk than was anticipated prior to the initiation of the trial. Unanticipated problems will also be reported within 14 days of the coordinating center learning about them to the DSMB and NHLBI.

[figure not shown]
#### **13.4.2 Grade 3 and 4 Clinical Adverse Events**

From Day 0 through Day 60, Clinical Adverse Events that are not PSESEs reaching Grade 3 or 4 severity level will be recorded on an eCRF. For a Clinical Adverse Event that was present at baseline, only those newly reaching Grade 3 or 4 will be recorded.

Clinical Adverse Events that are not PSESEs reaching Grade 3 or 4 severity level that occur between days 0 through 60 will be recorded on an eCRF at the time of phone follow-up. The date the event reaches the indicated grade will be collected to permit time-to-event analyses. These Clinical Adverse Events should be assessed for seriousness, relatedness, expectedness, severity (Section 13.3) and unanticipated problems. These events should be reported on the Adverse Event eCRF.

